The efficacy and safety of cabozantinib in combination with nivolumab (an anti-PD1 checkpoint inhibitor) as first line therapy in mRCC patients was investigated in the phase 3 CheckMate 9ER study. The combination met all efficacy endpoints and demonstrated superiority over sunitinib in PFS (median PFS 16.6 vs 8.3 month), OS and ORR [IV].

The combination of cabozantinib plus nivolumab was generally well tolerated, with a low rate of treatment-related discontinuations.

Furthermore, patients had significantly better quality of life with cabozantinib-nivolumab combination versus sunitinib. [IV]

The cabozantinib-nivolumab combination was submitted for regulatory approval to EMA. A positive CHMP opinion occurred in February 2021 and the Approval and Marketing Authorization by the European Commission was given on 31.03.2021.

Now as the cabozantinib-nivolumab combination is authorized for the European market, patients treated with this combination can be included in the Cabocare study as second treatment group.

Outside the setting of strictly controlled clinical studies there is only limited information about the efficacy and safety of cabozantinib or cabozantinib-nivolumab combination in the treatment of patients with advanced or metastasized renal cell carcinoma. Therefore, this non-

	
interventional study is planned to collect data of cabozantinib and cabozantinib-nivolumab combination usage in a real-life clinical setting taking into account the different prescribing physician groups (clinical oncologists and urologists as well as registered oncologists and urologists) in Germany and Austria.
 
[I] T. K. Choueiri et al., “Cabozantinib versus everolimus in advanced renal cell carcinoma (METEOR): final results from a randomised, open-label, phase 3 trial,” Lancet Oncol., vol. 17, no. 7, pp. 917–927, 2016.
 
[II] T. Powles et al., “European Association of Urology Guidelines for Clear Cell Renal Cancers That Are Resistant to Vascular Endothelial Growth Factor Receptor–Targeted Therapy,” Eur. Urol., vol. 70, no. 5, pp. 705–706, 2016.
 
[III] T. K. Choueiri et al., “Cabozantinib versus sunitinib as initial targeted therapy for patients with metastatic renal cell carcinoma of poor or intermediate risk: The alliance A031203 CABOSUN trial,” J. Clin. Oncol., vol. 35, no. 6, pp. 591–597, 2017.
 
[IV] T. K. Choueiri et al., ESMO 2020; oral presentation.

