	
As this is a non-interventional study, no formal statistical testing will be performed, and all the analyses will be primarily descriptive in nature. When appropriate and unless otherwise specified, 2-sided 95% confidence interval (CIs) will be displayed and if p-values are presented, they will be for exploratory purposes only.
 
Descriptive statistics will include number of available data, number of missing data and the following:
 

• Mean, standard deviation (SD), minimum, median, quartiles, maximum when appropriate for continuous variables;

• Frequency count and percentage for categorical nominal variables;

• Both the above for categorical ordinal variables.

 
All the analyses will be presented separately for each group, cabozantinib monotherapy and cabozantinib in combination with nivolumab.
 
Primary endpoint will be the descriptive analysis of the use of cabozantinib and the use of cabozantinib-nivolumab combination.
 
Secondary endpoints will be effectiveness (ORR, DCR and PFS). For secondary endpoints, the Kaplan-Meier method will be used to obtain the estimates of median PFS time and their associated 2-sided 95% CIs. For all other secondary objectives and safety events a descriptive analysis will be used. Analyses by risk groups will be performed for all endpoints where appropriate.

--	---

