### 4.1 Overview

This is an international, multicentre, non-interventional prospective study. Data will be collected via electronic case report form (eCRF) by the sites.

This study will be conducted in Germany and Austria, which have a cabozantinib tablets Marketing Authorisation (MA) for first line use. MA for the cabozantinib-nivolumab combination as first line treatment in advanced or metastatic RCC was in March 2021. Patients intended to be treated with this combination can be enrolled as soon as the MA is in place for use of these products in the European Union.

Investigators will follow their individual therapeutic concept for the treatment with cabozantinib or cabozantinib-nivolumab combination in accordance with the current SmPC.

No out-of-routine diagnostic or therapeutic intervention is allowed during this study. All data recorded in this study originate from routine diagnostic and therapeutic procedures.

The investigator needs to inform the subject that personal and medical data will be recorded for this study. The subject has to give written informed consent for data collection, data processing and for monitoring purposes.

Data will be collected at the described visits:

- Visit 1 (baseline): enrolment visit,
- Visit 2 (approximately 4 weeks after baseline),
- Visit 3 (approximately 8 weeks after baseline),
- Visit 4 (approximately 12 weeks after baseline),
- Visit 5 (approximately 16 weeks after baseline),
- Visit 6 (approximately 24 weeks after baseline),
- Visit 7 (approximately 32 weeks after baseline),
- Visit 8 (approximately 40 weeks after baseline),
- Visit 9 (approximately 48 weeks after baseline),
- Visit 10 (approximately 56 weeks after baseline),
- Follow-up 1 (30 days after treatment discontinuation),
- Follow-up 2 (1 year after treatment discontinuation or 24 months after baseline if subjects reached visit 10).

The timing of the visits according to routine clinical practice is assumed to be close to the proposed schedule. If the timing does not meet the schedule, entries should be made at the visit nearest in time to the proposed schedule.

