## **6 STUDY ASSESSMENTS**

Study Flow Chart [Table 2](#) shows the data that can be recorded in the eCRF at each of these visits.

Table 2 Flowchart

Visit	Visit 1 Baseline	Visit 2	Visit 3	Visit 4	Visit 5	Visit 6	Visit 7	Visit 8	Visit 9	Visit 10	Follow-up (FU) 1	FU 2
Assessment / Procedure	Day 1	4	8	12	16	24	32	40	48	56	30 days after TD	1 year after TD or 24 months after V1
Signature of informed consent	✓	informed consent must be signed prior to any documentation of data										
Visit date	✓	✓	✓	✓	✓	✓	✓	✓	✓	✓	✓	✓
Eligibility	✓											
Demographics (gender, year of birth)	✓											
Significant Medical or Surgical History	✓											
Disease history	✓											
Prior nephrectomies	✓											
Overall response		✓	✓	✓	✓	✓	✓	✓	✓	✓		
ECOG Performance Status	✓	✓	✓	✓	✓	✓	✓	✓	✓	✓		
Cabozantinib / cabozantinib-nivolumab regimen	✓	✓	✓	✓	✓	✓	✓	✓	✓	✓		✓*
Vital signs	✓	✓	✓	✓	✓	✓	✓	✓	✓	✓		
Inflammatory markers	✓			✓		✓		✓		✓		
Occupational status and smoking status	✓			✓		✓		✓		✓		
Quality of life questionnaire°	✓			✓		✓		✓		✓		
Activity questionnaire°	✓			✓		✓		✓		✓		
Actigraph measurement (1 week) °†	✓			✓		✓		✓		✓		
Adverse Events		✓	✓	✓	✓	✓	✓	✓	✓	✓	✓	✓
Concomitant medication for AEs		✓	✓	✓	✓	✓	✓	✓	✓	✓	✓	✓
Study discontinuation or completion form		✓	✓	✓	✓	✓	✓	✓	✓	✓	✓	✓
Post cabozantinib / cabozantinib-nivolumab systemic treatment for RCC											✓	✓

All data will be recorded as applicable and available: if a specific diagnostic procedure is done according to clinical routine the corresponding data should be recorded in the eCRF, otherwise the corresponding part of the eCRF will be marked as not done. TD: Treatment discontinuation, \*: only for subjects who have performed visit 10, °: not collected in eCRF, collected from patient by German Sport University Cologne; † only in centres where activity measurement is part of clinical routine

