### Visits 4/6/8/10 - (about 12, 24, 40 and 56 weeks, respectively, after baseline):

- Visit date

- Evaluation of tumour (Overall response)
- ECOG Performance Status
- Adverse Events
- Concomitant medication for AEs
- Cabozantinib regimen (Start date, stop date, dose, frequency, time of day of intake, primary reason for dose change or discontinuation).
- Nivolumab regimen (dose and date of injection, reason for injection delayed if any and primary reason for nivolumab discontinuation)
- Smoking status and Occupational status
- Vital Signs (Body weight, blood pressure)
- Inflammatory blood markers (hsCRP or CRP, as available, no safety marker)
- Quality of life questionnaire (NFKSI-19) after the visit
- Activity questionnaire after the visit
- Actigraph measurement (1 week) after the visit [only in centres where activity measurement is part of clinical routine]
- Study discontinuation or completion form (in case of discontinuation: reason for premature withdrawal)

Follow-up visit (FU) 1 - (about 30 days after treatment discontinuation):

- Visit date
- Adverse Events
- Concomitant medication for AEs
- Post Cabozantinib / cabozantinib-nivolumab combination systemic treatment for RCC
- Study discontinuation or completion form (in case of discontinuation: reason for premature withdrawal)

Follow-up visit (FU) 2 - (1 year after treatment discontinuation or 24 months after visit 1):

- Visit date
- Adverse Events
- Concomitant medication for AEs
- Post Cabozantinib /cabozantinib-nivolumab combination systemic treatment for RCC
- Cabozantinib regimen (dose and date for last cabozantinib intake; only for patients who continued until visit 10)
- Cabozantinib-nivolumab combination regimen (dose and date for last cabozantinib and nivolumab intake; only for patients who continued until visit 10)
- Study discontinuation or completion form (in case of discontinuation: reason for premature withdrawal)

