##### *9.4.4.2 Secondary Endpoint Analysis*

The secondary endpoints will be analysed descriptively by risk group and overall.

ORR and DCR will be described at each time point (W8, W16, W24, W32, W40, W46 and W52). The progression free survival, defined as time from cabozantinib /cabozantinib-nivolumab combination initiation to disease progression or death will be analysed using standard survival analysis methods including Kaplan-Meier product-limit survival curve. The median time to event will be estimated and presented with its 95% confidence interval.

The subjects still alive without disease progression at the end of the follow-up will be censored at their last assessment date.

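### In the combination group, the planned median PFS probably falls after the last point at which progression is recorded

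*Protocol*

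**What the plan says.** **Endpoint and estimate.** Section 7.1.2 defines PFS as time from treatment start to progression (RECIST 1.1 or clinical) or death from any cause, with no time limit on deaths. The Synopsis states that "the Kaplan-Meier method will be used to obtain the estimates of median PFS time", and Section 9.4.4.2 repeats the plan for a median with a 95% confidence interval. The censoring rule there is: "The subjects still alive without disease progression at the end of the follow-up will be censored at their last assessment date". It does not say which kind of assessment is meant.

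**When progression can be recorded.** Section 6 says that Table 2 "shows the data that can be recorded in the eCRF at each of these visits". In Table 2 the row "Overall response" is ticked at Visits 2 to 10 and blank at both follow-up visits. Section 6.1 agrees: the item "Evaluation of tumour (Overall response" is listed for every visit from 2 to 10 and for neither follow-up visit. The last of these visits is "Visit 10 (approximately 56 weeks after baseline".

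**Early stops.** Under Section 4.1, a subject who stops before Visit 10 goes directly to Follow-up 1. For the combination, a stop means that both drugs have been permanently discontinued.

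**End of follow-up.** The last contact is "Follow-up visit (FU) 2 - (1 year after treatment discontinuation or 24 months after visit 1". For a subject who reached Visit 10 this is month 24, with no scheduled contact in between unless treatment stops. Follow-up 2 lists adverse events, concomitant medication, later systemic therapy, dose and date of last intake, and the discontinuation form.

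**Deaths.** The Synopsis lists vital status as an effectiveness item, Section 5.3 lists death as a withdrawal reason, and Table 2 ticks adverse events and the discontinuation form at Follow-up 2. Section 7.2 ends the collection of adverse events and deaths at Follow-up 1.

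**Expected PFS.** For the combination, the Synopsis cites "median PFS 16.6 vs 8.3 month" against the comparator and an expected median treatment duration of about 14 months. The only PFS planning figure, in Section 9.3, is 35% at 12 months, from the former 100-subject monotherapy target.

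**The concern.** A median can be estimated only if the curve reaches 50% while events are still being observed. Both combination figures in the protocol, 16.6 months for PFS and 14 months for treatment, lie beyond 12.9 months. Progression after week 56, or after both drugs are stopped, has no field on the eCRF as described, while follow-up continues and deaths may still be picked up.

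The analysis would then join two observation windows: a short one for progression and a longer one for death. What that does to the curve depends on two points that the protocol leaves open: what the last assessment is, and whether a death long after the last tumour evaluation is an event. At stake is the published combination median PFS, one of the study's secondary effectiveness results. The primary endpoints (adverse-event-related dose changes and stops) are not affected.

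**Working it through.** **1. The protocol's own PFS figure.** For 35 of 100, the exact (Clopper-Pearson) 95% interval is 0.257 to 0.452, as Section 9.3 states. That figure reproduces.

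**2. Length of the window.** 56 weeks × 7 / 30.44 = 12.9 months.

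**3. Where the combination median falls.** With exponential PFS, S(t) = 0.5^(t/median).
- S(12.9) = 0.5^(12.88/16.6) = 0.584, so about 58% are event-free at week 56.
- The median comes 16.6 − 12.9 = 3.7 months after the last recordable tumour evaluation.
- With a 14-month median treatment duration, 0.5^(12.88/14) = 0.53 are still on treatment at week 56.
- True S(24) = 0.5^(24/16.6) = 0.37.

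**4. Where the monotherapy median falls.** 35% at 12 months gives 12 × ln 2 / (−ln 0.35) = 7.9 months, inside the window.

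**5. What each reading would report for the combination.** Kaplan-Meier simulation with N = 167 and 400 runs per scenario. These inputs are assumptions and are not in the documents: exponential PFS with median 16.6 months; 24-month overall survival of 60, 70 or 80%; 10 or 20% of PFS events are deaths without progression; exponential post-progression survival. A seventh scenario adds full treatment stops for toxicity, at a rate derived from 15.3% over 14 months.

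| Handling | Median PFS (months) | Runs reaching the median | S(18) | S(24) |
|---|---|---|---|---|
| Truth (progression recorded to month 24) | 16.3–16.6 | 100% | 0.47 | 0.37 |
| A. Censor at last tumour assessment, count deaths to Follow-up 2 | 14.4–15.8 | 100% | 0.31–0.40 | below 0.01 |
| B. Censor at Follow-up 2 | 23–24 or not reached | 16–63% | 0.55–0.58 | 0.49–0.54 |
| C. Censor at last tumour assessment, later deaths not counted | rarely reached | 1–4% | curve ends at 12.9 months, about 0.58 | – |

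The directions follow from the schedule. Under A, event-free survivors leave the risk set by week 56 and those who will die stay in it, so the tail can only fall. Under B, unrecorded progressions count as progression-free time. Under C, the curve is sound as far as it goes but usually stops above 50%.

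**6. The same check for monotherapy.** With a median of 7.9 months, 24-month overall survival of 50% and 10% direct deaths, the median is 7.9 months under A, B and C. With N = 35 it is 7.8 under all three, against a true 7.8. Only the tail moves: with the larger N, S(24) is 0.003 under A and 0.26 under B, against a true 0.125.

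**7. Dependence on the cited median.** If the real-life combination median were 12 months (24-month overall survival 65%, 10% direct deaths), A and B would both give 12.0, and C would reach the median in 72% of runs.

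**The case against.** **The SAP can settle the censoring rule.** Section 9.4 assigns derivation and missing-data rules to the SAP, so an undefined last assessment date alone would not be a finding. That stands. But an SAP can only choose among readings A, B and C; it cannot supply progression dates that were not collected.

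**Progression may surface elsewhere.** The reason for stopping treatment is recorded at Visits 2 to 10, and later therapy or a fatal event may point to progression. None of these gives a progression date in follow-up, and progression is not among the withdrawal reasons in Section 5.3. The rule of entering data at the nearest visit does not help: a scan at month 18 has no nearby visit with a tumour field.

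**The 16.6 months come from a controlled trial.** The protocol adopts no PFS assumption for the combination. That stands, and is why the heading says probably. Step 7 shows that the problem shrinks if the real median is shorter.

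**The shift under A is small.** About 167 × (1 − 0.367) = 106 events by month 24 give an approximate 95% interval of 16.6 × exp(±1.96/√106), or 13.7 to 20.1 months. The 14.4 to 15.8 months under A lie inside it. That is fair for a single study, but the error is systematic, and the curve's tail is far off.

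**PFS is secondary and descriptive.** True: it is listed beside ORR and DCR, with no formal testing. The median would still be reported.

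A reader might go further and infer that the whole Kaplan-Meier analysis is wrong beyond month 13 in both groups because deaths count to month 24. The documents do not support that. Deaths counting to month 24 is an inference that Section 7.2 contradicts; reading C truncates the curve and does not distort it; and the monotherapy median lies inside the window. A reader might also take the 15.3% in Section 9.3 as the share lost to tumour follow-up through toxicity. That figure is for stopping either drug, whereas Section 4.1 keeps a subject on scheduled visits until both are stopped.

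**Conclusion.** The point holds for the combination group. On the protocol's cited median, and assuming exponential PFS, about 58% would be event-free when tumour recording ends at 12.9 months, and the planned median lies about 3.7 months later. No handling of the existing data recovers it reliably:

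- if deaths after the last tumour assessment are not counted, it is reached in 1–4% of simulated studies;
- if subjects are censored at Follow-up 2, it is biased upward or not reached (reached in 16–63%);
- if subjects are censored at the last tumour assessment while deaths to Follow-up 2 count, it is biased downward to 14.4–15.8 months, with a tail near zero at month 24 against a true 0.37.

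The exact sizes rest on the stated survival assumptions; the directions do not. Week 56 is the latest point at which recording ends: a subject who stops all treatment before progression leaves tumour observation at once, and that censoring may be informative. The documents give no rate for such stops.

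The monotherapy median is largely unaffected by the week-56 cut-off; only its tail is. Separately, Section 7.2 conflicts with the Synopsis, Section 5.3, Table 2 and the Follow-up 2 list on whether deaths are collected after Follow-up 1, and these must be reconciled.

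**What to change.** **Data capture.** Add to the Follow-up 1 and Follow-up 2 eCRF pages, from routine records only:
- progression since the last visit (yes/no, date, radiological or clinical);
- date of the last tumour assessment;
- vital status, with date of death.

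This requires no procedure outside routine care, so it respects Section 4.1. Bring Section 7.2 into line with Table 2 and Section 6.1 on deaths after Follow-up 1.

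**Section 9.4.4.2.** Define the last assessment as the last tumour assessment, and state how a death after a gap in tumour assessment is treated.

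**If the eCRF is not changed.** Censor at the last tumour assessment, no later than week 56. Report the 12-month PFS rate as the main combination summary instead of the median; 12 months lies inside the window, and Section 9.3 already uses that quantity. This does not repair the loss of tumour data at earlier stops, so the report should say that censoring at treatment stop before progression may be informative.

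**Cost.** A few eCRF fields, one retrospective chart query for subjects already in or past follow-up, and two sentences in Section 9.4.4.2. Last subject last visit is planned for Q2 2027.

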##### *9.4.4.3 Exploratory Endpoint Analysis*

The evolution of activity level and quality of life between baseline and each time point (W12, W24, W40 and W56) will be described overall and also according to occupational and smoking status at initiation of Cabozantinib /cabozantinib-nivolumab combination in centers where this is part of the clinical routine.

Concomitant medications to cope with treatment related adverse event will be presented by therapeutic group and preferred name.

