### Visit 1, baseline (enrolment):

- Date of informed consent signature
- Visit date
- Eligibility (verification of in- and exclusion criteria)
- Demographics (gender, year of birth)
- Significant Medical or Surgical History
- Disease history (date of renal cell carcinoma diagnosis, RCC stage at diagnosis, RCC stage at baseline (TNM), cancer histology, risk score either by IMDC or MSKCC)
- Prior Nephrectomies (occurrence and date)
- ECOG Performance Status
- Smoking status and Occupational status
- Vital Signs (Height and body weight, blood pressure)
- Inflammatory blood markers (hsCRP or CRP, as available, no safety marker)
- Quality of life questionnaire (NFKSI-19) after Visit 1 (within 2 weeks)
- Activity questionnaire after Visit 1 (within 2 weeks)
- Actigraph measurement (1 week) after Visit 1 (within 2 weeks) [only in centres where activity measurement is part of clinical routine]

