### **6.2.3 Actigraph measurement**

The Actigraph is the most frequently used tool to objectively assess physical activity in clinical and non-clinical studies. In detail, the Actigraph GT9X Link device will record raw data on physical activity (acceleration), steps, intensity of physical activity and body position.

The device will be worn by all subjects up to five times (less in case of early treatment discontinuation) for one week (seven days) after the respective visits. After wearing the device for one week, patients will complete the questionnaires listed under [6.3.1](#) and [6.3.2](#). After completing Visit 10 or after cabozantinib treatment discontinuation, subjects and the respective treating physician will receive a detailed report on their physical activity behaviour together with exercise recommendations. The Actigraph will only be used in centres where activity measurement is part of clinical routine.

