### **6.2.4 Handling of device and questionnaires**

The device (Actigraph) and the questionnaires will be sent to the subjects first after informed consent (Visit 1) and thereafter at the respective weeks of Visit 4, 6, 8 and 10 (see [Table 2](#)). The subjects will receive a package from the researcher (German Sport University Cologne) including the device with an instruction and a help desk number, as well as the two questionnaires and a return package. After one week the subject will fill out the questionnaire and send the device and the questionnaires in the provided return package back to the vendor. The researcher will follow up with the subject if package is not received. Data handling is described in [12.3](#).

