### 7.1.2 *Secondary Endpoints & Evaluations*

- To describe the effectiveness of cabozantinib /cabozantinib-nivolumab combination in advanced or metastatic RCC in real-life in terms of progression free survival (PFS), and best overall response (ORR & DCR).
  - Progression free survival is defined as the time between the start date of cabozantinib /cabozantinib-nivolumab combination and the date of progression or death from any cause. Disease progression is defined as either radiological progression assessed by the investigator using RECIST 1.1 [7] or clinical progression.
  - The best overall response is the best response assessed by investigator recorded during the treatment period.
  - ORR is defined as the proportion of subjects achieving complete or partial response.
  - DCR is defined as the proportion of subjects achieving a complete response, partial response or stable disease.
- To describe the impact of the activity level at the beginning of the treatment (within the first 2 weeks of cabozantinib /cabozantinib-nivolumab combination intake) on the occurrence of adverse events (AEs) using the actigraph and questionnaires
- To describe the use of cabozantinib /cabozantinib-nivolumab combination in subjects with advanced or metastatic renal cell carcinoma (mRCC) treated in real-life clinical setting in 1st line treatment split by histological subtype (clear cell and non-clear cell) in terms of:
  - Number and proportion of subjects with dose reductions of cabozantinib due to SAEs/AEs
  - Number and proportion of subjects with dose interruption of cabozantinib and/or nivolumab due to SAEs/AEs
  - Number and proportion of subjects with termination of cabozantinib /cabozantinib-nivolumab combination due to SAEs/AEs
  - Number and proportion of subjects with injection delayed of nivolumab due to SAEs/AEs

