**Appendix 1 NCCN-FACT FCSI-19 questionnaire**

NCCN-FACT FKSI-19 (Version 2)

Date: \_\_\_\_\_

Patient ID: \_\_\_\_\_

Signature: \_\_\_\_\_

Below is a list of statements that other people with your illness have said are important. Please circle or mark one number per line to indicate your response as it applies to the past 7 days.

		Not at all	A little bit	Some-what	Quite a bit	Very much	
D R S- P	GP1	I have a lack of energy.....	0	1	2	3	4
	GP4	I have pain .....	0	1	2	3	4
	C2	I am losing weight .....	0	1	2	3	4
	HP7	I feel fatigued.....	0	1	2	3	4
	B1	I have been short of breath .....	0	1	2	3	4
	HRM3	I am bothered by fevers (episodes of high body temperature).....	0	1	2	3	4
	HP1	I have bone pain .....	0	1	2	3	4
	L2	I have been coughing.....	0	1	2	3	4
	HE12	I feel weak all over .....	0	1	2	3	4
	RCC 2	I have had blood in my urine.....	0	1	2	3	4
	C6	I have a good appetite.....	0	1	2	3	4
	D R- S- E	GP5	I am sleeping well.....	0	1	2	3
GP6		I worry that my condition will get worse .....	0	1	2	3	4
GP2		I have nausea .....	0	1	2	3	4
T S E	C3	I have diarrhea (diarrhoea) .....	0	1	2	3	4
	GP5	I am bothered by side effects of treatment ....	0	1	2	3	4
F W B	GP1	I am able to work (include work at home) ....	0	1	2	3	4
	GP3	I am able to enjoy life.....	0	1	2	3	4
	GP7	I am content with the quality of my life right now.....	0	1	2	3	4

DRS-P=Disease-Related Symptoms Subscale - Physical  
 DRS-E=Disease-Related Symptoms Subscale - Emotional  
 TSS=Treatment Side Effects Subscale  
 FWB=Function and Well-Being Subscale  
 English (Universal)  
 Copyright 2001

All translations, adaptations, symptom indices, computer programs, and scoring algorithms, and any other related documents of the Functional Assessment of Chronic Illness Therapy (FACIT) Measurement System, including the Functional Assessment of Cancer Therapy (FACT), are owned and copyrighted by, and the intellectual property of, [name]. Copyright protection is also extended to electronic versions of all FACIT documents and products. By downloading documents from this website, you agree to the following:

No changes to the wording or phrasing of any FACIT document can occur without written

permission. If any changes are made to the wording or phrasing of any FACIT item without permission, the document cannot be considered the FACIT, and subsequent analyses and/or comparisons to other FACIT data will not be considered appropriate.

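### The quality-of-life score used as baseline is collected up to two weeks after Visit 1 with a 7-day recall, so it may describe days on treatment, in a proportion that varies between subjects

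*Protocol*

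**What the plan says.** Section 9.4.4.3 of the protocol plans the description of quality of life over time: "The evolution of activity level and quality of life between baseline and each time point (W12, W24, W40 and W56) will be described". Table 2 places the first FKSI-19 at Visit 1 and the next at Visit 4 (week 12), so the Visit 1 form is the only candidate for baseline.

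The timing of that form is set in several places:

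- Section 6.1, Visit 1: "Quality of life questionnaire (NFKSI-19) after Visit 1 (within 2 weeks").
- Section 6.2.4, on dispatch: the device and questionnaires "will be sent to the subjects first after informed consent (Visit 1"). On completion: "After one week the subject will fill out the questionnaire and send the device and the questionnaires in the provided return package".
- Section 6.2.3 gives the same order: "After wearing the device for one week, patients will complete the questionnaires". It restricts the device to centres where activity measurement is routine.
- Appendix 1, on recall: subjects are to "indicate your response as it applies to the past 7 days".
- Section 7.1.2, on the activity level measured with the same package: "at the beginning of the treatment (within the first 2 weeks of cabozantinib /cabozantinib-nivolumab combination intake").

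Inclusion criteria 2a and 3a cover subjects receiving the treatment and subjects intended to receive it. No section ties the first dose to Visit 1 or to completion of the form.

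**The concern.** A baseline for change over treatment should describe the subject before treatment. Here the form reaches the subject only after enrolment and looks back 7 days, while treatment may already have begun. Section 7.1.2 treats the matching activity window as time on drug, yet section 9.4.4.3 calls the score baseline.

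Section 7.1.3 names the FKSI-19 total and its four subscores as measures for the exploratory objective on coping with treatment-related adverse events. The treatment side effects subscale has three items: nausea, diarrhoea and being bothered by side effects. Section 2.1 lists nausea and diarrhoea among the main adverse events of cabozantinib. This subscale is therefore the most exposed to a reference taken on drug. A subject whose early toxicity persists could show no change from such a reference, and one whose early toxicity resolves could show a gain.

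**Working it through.** The protocol gives no sample size, effect size or precision for the FKSI-19, so there is no stated figure to reproduce. The check is a timeline.

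**Inputs.** Visit 1 is day 1 (Table 2). Completion follows 7 days of wear (6.2.3, 6.2.4) and falls within 2 weeks after Visit 1 (6.1). Recall is 7 days (Appendix 1). Two inputs are assumptions: postage of 0 to 3 days, and the day of first dose.

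**Completion day.** c = 1 + (0 to 3) + 7 = day 8 to 11. The recall window is days c − 7 to c − 1, that is days 1–7 at the earliest and days 4–10 at the latest.

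**On-drug recall days.** With first dose on day d, n = max(0, min(7, c − d)).

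| First dose | c = 8 | c = 9 | c = 10 | c = 11 |
|---|---|---|---|---|
| Day 1 or earlier | 7 | 7 | 7 | 7 |
| Day 4 | 4 | 5 | 6 | 7 |
| Day 8 | 0 | 1 | 2 | 3 |

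**Edges of the window.** With treatment starting at or before Visit 1, n stays at 7 for every completion from 7 to 14 days after Visit 1. A wholly pre-treatment score is guaranteed at every permitted completion time only if the first dose comes 14 or more days after Visit 1. Without the device, the one-week minimum may not apply. Completion 3 days after Visit 1 (c = 4), with first dose on day 1, gives n = 3, or 3/7 = 43% of the recall window.

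**Effect on the reported change.** Let T be the change from the pre-treatment state to week 12, and E the part of any early change already reflected in the Visit 1 score. The reported change is T − E. If E = g × T, the reported change is (1 − g) × T: 75%, 50% or 25% of T for g = 0.25, 0.50 or 0.75. If E and T have opposite signs, the reported change is larger in size than T. The protocol gives no value for g or for the sign of E, so these are illustrations only.

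**The case against.** The strongest reply is that the protocol never ties the first dose to Visit 1. Subjects who are only scheduled for treatment at enrolment may start a week or more later and give a largely or wholly pre-treatment score. The two-week statement in section 7.1.2 is written for activity level, not for quality of life. This stands in part. A reader might infer that most subjects have no pre-treatment FKSI-19, but that depends on start dates which the protocol does not give. What remains is that the FKSI-19 travels in the same package, that nothing schedules it before the first dose, and that the share of recall on drug is uncontrolled.

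A second reply concerns direction. A reader might infer that the plan hides an initial fall and so understates deterioration. The protocol contains no early FKSI-19 data to support this. Twelve of the 19 items are physical disease symptoms, which may improve on treatment, and three are treatment side effects. Loss of early change is supported; its sign is not.

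A third reply is that section 9.4 leaves derivation rules to the SAP, which is not at hand. A SAP could set the labelling rule. It could not create a pre-treatment score, because the protocol fixes when the form is sent and completed.

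Finally, this is one descriptive exploratory measure in a study without formal testing. That is correct and limits the weight of the point.

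**Conclusion.** The point holds in a limited form. Followed as written, the protocol gives a quality-of-life reference that is on treatment for some subjects and mixed for others, and section 9.4.4.3 calls it baseline without distinction. All 7 recall days are on drug when treatment starts at or before Visit 1 and the form follows the wear week. The mixed cases depend on the assumed postage and first-dose day. The share of subjects affected, and the size and direction of the effect on the reported evolution, cannot be derived from the protocol. The primary endpoint, progression-free survival, response and adverse event incidence are unaffected. The point is confined to quality of life and does not address the planned description of adverse events by activity level.

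**What to change.** In section 9.4.4.3, classify each Visit 1 FKSI-19 by its completion date against the date of first dose. Call it baseline only if it was completed on or before the first dose; otherwise call it early on-treatment (weeks 1–2). Present the evolution to weeks 12, 24, 40 and 56 separately for the two groups, with the number of subjects in each. Do not describe change from the early on-treatment score as change from a pre-treatment baseline. The form carries a date (Appendix 1) and the eCRF records the regimen dates (section 6.1), so no new data are needed.

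For subjects still to be enrolled who have not started treatment, amend sections 6.1 and 6.2.4 so that the same paper form is provided for completion before the first dose where feasible, with no change to when treatment starts.

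The costs are modest but real. Few of the subjects already enrolled may have a true baseline, and those who do may be a selected group that started late after enrolment. Completion before the first dose is impossible for subjects already on drug under criterion 2a. Because the forms are now posted by the external university, earlier completion needs a small change in how they are handed out.
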